7.3.2.2 Clinical Laboratory Investigations

Laboratory tests will be performed for all patients during treatment, the Post-treatment Follow-up Visit, and if toxicities are present, according to institutional standard of care practices, per investigator.

Pregnancy testing for WOCBP must be reviewed by the investigator before the start of treatment with rucaparib and ongoing throughout the study when testing occurs.

Data will be recorded in source documentation at the site and not entered into the eCRF. SAEs/AESIs will be reported to the sponsor and captured in the Clovis PV database.

Additional and more frequent tests may be performed at the investigator's discretion.

In studies treating female patients:

Pregnancy Test: Female patients of childbearing potential must have a pregnancy test result \leq 3 days prior to first dose of rucaparib in this study (a negative result is required before

dosing can begin), ≤ 3 days prior to Day 1 of every cycle during treatment, and at the Post-treatment Follow-up Visit. A positive pregnancy test during participation in the treatment phase of the study must be reported to the sponsor. Refer to Section 8.5 for details.

Local laboratory reports should be reviewed by the investigator or delegated physician.

7.3.3 Long-term Follow-up Data

Patients will be followed approximately every 12 weeks for collection of LTFU data until death, lost to follow-up, withdrawal of consent, or until closure of this study by the sponsor, as applicable based on parent study objectives.

Date and cause of death will be recorded in the Death eCRF provided by the sponsor.

8 ADVERSE EVENT MANAGEMENT

8.1 Definition of an Adverse Event

An AE is defined as any untoward medical occurrence in a patient administered a medicinal product that does not necessarily have a causal relationship with this treatment. An AE can, therefore, be any unfavorable and unintended sign (including an abnormal laboratory finding), symptom, or disease temporally associated with the use of an investigational product, whether or not related to the investigational medicinal product. This includes an exacerbation of pre-existing conditions or events, intercurrent illnesses, drug interaction, or the significant worsening of the indication under investigation that is not recorded elsewhere on the eCRF under specific efficacy assessments. Anticipated fluctuations of pre-existing conditions, including the disease under study, that do not represent a clinically significant exacerbation or worsening are not considered AEs.

It is the responsibility of the investigator to monitor all AEs that occur during the study. AEs should be elicited by asking the patient a non-leading question (eg, "Have you experienced any new or changed symptoms since we last asked/since your last visit?"). The existence of an AE may be concluded from a spontaneous report of the patient; from the physical examination; or from special tests such as the ECG, laboratory assessments, or other study-specified procedure (source of AE). Symptoms reported spontaneously by the patient during the physical examination would also qualify as an AE.

8.2 Definition of a Serious Adverse Event

An SAE is any untoward medical occurrence that occurs at any dose (or, occurs after informed consent is given and prior to dosing if the SAE is related to a study procedure) that:

• Results in death. Any event resulting in death during the reporting period (from date of first dose of investigational product through 28 days after last dose) must be treated as an SAE and reported as such. An event related to a study procedure that occurs after informed consent, but prior to dosing that results in death must also be reported as an SAE;

- Is life-threatening (patient is at immediate risk of death from the event as it occurred);
- Requires in-patient hospitalization (formal admission to a hospital for medical reasons) or prolongation of existing hospitalization;
- Results in persistent or significant disability/incapacity;
- Results in a congenital anomaly or birth defect; or
- Is an important medical event that may not result in death, is not life-threatening, or does not require hospitalization but may be considered an SAE when, based on appropriate medical judgment, it may jeopardize the patient and may require medical or surgical intervention to prevent one of the outcomes listed in this definition. Examples of such events include allergic bronchospasm requiring intensive treatment in an emergency room or at home or the development of drug dependency or drug abuse.

8.3 Definition of an Adverse Event of Special Interest

Adverse events of special interest (AESIs, serious or nonserious) are defined as AEs of scientific and medical concern specific to the sponsor's product or program, for which ongoing monitoring and rapid communication by the investigator to the sponsor can be appropriate. Such an event might warrant further investigation in order to characterize and understand it. Depending on the nature of the event, rapid communication by the study sponsor to other parties (eg, regulators) might also be warranted.

Details on the sponsor's currently agreed list of AESIs for rucaparib can be found in the current rucaparib IB. These AESIs are to be reported to the sponsor **within 24 hours** of knowledge of the event (see Section 8.6 for reporting instructions).

Report any AE of pneumonitis, or any of the following AEs, irrespective of causality assessment and severity, as an AESI within 24 hours using the study Serious Adverse Event Form and the applicable procedures as outlined in Section 8.6:

- Pneumonitis
- Interstitial lung disease
- Pulmonary fibrosis
- Acute interstitial pneumonitis
- Alveolitis necrotizing
- Alveolitis
- Hypersensitivity pneumonitis
- Organizing pneumonia

8.4 Events or Outcomes Not Qualifying as Serious Adverse Events

The following are not considered SAEs and therefore do not need to be reported as such:

- Pre-planned or elective hospitalization including social and/or convenience situations (eg, respite care);
- Hospital visits of less than 24 hours duration (eg, patient presents to the emergency room, but is not admitted to a ward);
- Overdose of either investigational product or concomitant medication unless associated with an SAE. However, the event should still be captured as a nonserious AE on the appropriate eCRF page;
- Events of progression of the patient's underlying cancer as well as events clearly related to progression of the patient's cancer (signs and symptoms of progression) should not be reported as an AE or SAE; and
- Events that meet the SAE criteria (as outlined in Section 8.2) and occur after informed consent but before the first dose of investigational product, which are considered unrelated to protocol-mandated screening procedures.

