3.2.1 Treatment Phase

The starting dose of rucaparib administered at initiation of this study will be the same as the last dose received in the parent study, or as deemed appropriate by the investigator and based on available dose strength tablets. The first treatment in the rollover study will begin at the next scheduled treatment visit following the EOT Visit in the parent study.

Safety and disease assessments should be performed according to institutional standard of care practices. Suggested assessments include monitoring for adverse events (AEs), complete blood count, pregnancy test for women of childbearing potential (WOCBP; required), disease assessments, laboratory assessments (clinical chemistry, urinalysis), vital signs, and rucaparib accountability (required). See Section 7.1.

Patients enrolled to receive continued rucaparib may be treated until disease progression, as assessed by the investigator, unacceptable toxicity, withdrawal of consent, death, loss to follow-up, or study closure by the sponsor.

If a patient demonstrates disease progression per investigator assessment while receiving treatment with rucaparib but continues to derive clinical benefit, then continuation of treatment beyond progression is permitted based on investigator decision and patient consent. If a patient continues treatment post-progression, all study assessments should be continued per institutional standard of care. The patient should be discontinued from treatment once it is clear that no further clinical benefit can be achieved.

The first and last dates of dosing should be captured in the electronic Case Report Form (eCRF). SAEs and AESIs will be reported per Clovis Pharmacovigilance (PV) guidelines and captured in the Clovis PV database.

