7.3 Methods of Data Collection

SAEs and AESIs that occur after informed consent will be collected through 28 days after the last dose of rucaparib for patients receiving treatment in this study. Only SAEs/AESIs will be reported in the Clovis PV database.

After the 28-day Post-treatment Follow-up Visit, only SAEs considered as potentially related to rucaparib should be reported per Clovis PV requirements and captured in the Clovis PV database. This includes serious reports of pneumonitis or associated events, if considered to be related to study drug.

After the 28-day Post-treatment Follow-up Visit, AESIs of MDS and AML, irrespective of causality, should be reported per Clovis PV requirements and captured in the Clovis PV database.

• AESIs of pneumonitis or associated events should only be reported up to, but not beyond, the Post-treatment Follow-up Visit (28-days after the last dose of rucaparib).

Hematology, clinical chemistry, urinalysis, vital signs, and disease assessments should be performed locally per institutional standard of care practices. Pregnancy testing will be performed locally per institutional standard of care at screening (the EOT Visit of parent study), before initiation of each treatment cycle, and at the Post-treatment Follow-up Visit of this study.

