7.3.2 Safety Evaluations

7.3.2.1 Adverse Event Assessment

The investigator has the responsibility for assessing the safety of the patients, including monitoring and management of all AEs experienced, and for compliance with the protocol to ensure study integrity. Only SAEs and AESIs occurring from the time of informed consent through 28 days after the last dose of rucaparib will be reported in the Clovis PV database.

After the post-treatment 28-day follow-up window, only SAEs considered as potentially related to study drug should be reported per Clovis PV requirements and captured in the Clovis PV database. This includes serious reports of pneumonitis or associated events, if considered to be related to study drug.

After the 28-day Post-treatment Follow-up Visit, AESIs of MDS and AML, irrespective of causality, should be reported per Clovis PV requirements and captured in the Clovis PV database.

• AESIs of pneumonitis or associated events should only be reported up to, but not beyond, the Post-treatment Follow-up Visit (28-days after the last dose of rucaparib).

Any ongoing SAEs and AESIs will be followed until resolution or stabilization.

If a patient discontinues from treatment in the rollover study and begins a subsequent anticancer therapy, the sponsor will terminate collection of SAEs.

Complete details for monitoring AEs, including the definition of drug-related AEs, are provided in Section 8.

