8.6 Recording of Serious Adverse Events and Adverse Events of Special Interest

Any SAE/AESI that occurs after signing informed consent through 28 days after receiving the last dose of investigational product is to be reported to the sponsor and captured in the PV database.

After the 28-day Post-treatment Follow-up Visit, only SAEs assessed as potentially related to study drug should be reported per Clovis PV requirements and captured in the Clovis PV database. This includes serious reports of pneumonitis or associated events, if considered to be related to study drug.

After the 28-day Post-treatment Follow-up Visit, AESIs of MDS and AML, irrespective of causality, should be reported per Clovis PV requirements and captured in the Clovis PV database.

• AESIs of pneumonitis or associated events should only be reported up to, but not beyond, the Post-treatment Follow-up Visit (28-days after the last dose of rucaparib).

Information on the follow-up of SAEs, and AESIs is provided in Section 8.7.

In order to avoid vague, ambiguous, or colloquial expressions, the AE should be recorded in standard medical terminology rather than the patient's own words. Whenever possible, the investigator should combine signs and symptoms that constitute a single disease entity or syndrome into a final diagnosis, if appropriate. For example, fever, cough, and shortness of breath may be reported as pneumonia, if that is a reasonable diagnosis.

Each SAE is to be evaluated for causal relationship to the investigational drug, severity, and seriousness. The action taken, and the outcome must also be recorded.

SAEs and AESIs that occur during the study or within 28 days after receiving the last dose of investigational product, whether or not related to investigational product, must be reported immediately (ie, **within 24 hours** of knowledge of the event or additional information for a previously-reported event) to the sponsor/SAE designee. The contact information for reporting of SAEs/AESIs can be found on the SAE/AESI Reporting Form.

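### Sections 8.2/8.4 and 7.3/8.6 start SAE reporting at different points, so a serious rucaparib-related event that is not an AESI may not be reportable between rollover consent and first rollover dose

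*Protocol*

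**What the plan says.** Three places in the Protocol set the start of safety reporting at informed consent. Section 7.3: "SAEs and AESIs that occur after informed consent will be collected through 28 days after the last dose of rucaparib". Section 8.6: "Any SAE/AESI that occurs after signing informed consent through 28 days after receiving the last dose of investigational product is to be reported"; the same section asks for 24-hour reporting regardless of causality. Section 7.3.2.1 gives the same window in the form of a limit: "Only SAEs and AESIs occurring from the time of informed consent through 28 days after the last dose of rucaparib will be reported".

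Two other places cut that window back before dosing. Section 8.2 recognises an SAE in the pre-dose period only where it "occurs after informed consent is given and prior to dosing if the SAE is related to a study procedure", and it describes the reporting period for events resulting in death as running "from date of first dose of investigational product through 28 days after last dose", with an exception for procedure-related deaths after consent. Section 8.4 opens its list with "The following are not considered SAEs and therefore do not need to be reported as such", and its last bullet covers events that "occur after informed consent but before the first dose of investigational product, which are considered unrelated to protocol-mandated screening procedures".

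On timing, section 3.2 has treatment patients consent before the parent study's end-of-treatment (EOT) visit, and section 3.2.1 adds: "The first treatment in the rollover study will begin at the next scheduled treatment visit following the EOT Visit in the parent study".

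**The concern.** A carve-out for unrelated pre-dose events suits a trial of untreated patients, where nothing before the first dose can be a drug effect. Here, inclusion criterion 2a requires treatment patients to be on rucaparib already, and the synopsis anticipates roughly 6 months or more of prior exposure. A serious event between rollover consent and the first rollover dose can therefore be caused by the drug, yet the only test in 8.2 and 8.4 is relation to a procedure. The rollover study has few procedures of its own at that stage: Table 7-1 shows consent, plus a pregnancy test for women of childbearing potential. Most serious events in the interval would fall under the exclusion.

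Collecting SAEs and AESIs is one of the study's three objectives. There is no data monitoring committee (3.3), and expedited reporting under 8.9 depends on sites submitting events. A site that follows 8.4 and a site that follows 8.6 would handle the same event differently.

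**Working it through.** The plan gives no figure to reproduce, and no sample-size or error-rate calculation applies. The check sets the rules side by side for a continuing-treatment patient with an event after rollover consent and before the first rollover dose.

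**Step 1. What each rule does if first dose means first dose in this study.**

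| Event in the interval | 8.2 / 8.4 | 7.3 / 8.6 | Agree? |
|---|---|---|---|
| Serious, related to a screening procedure | SAE | Report | Yes |
| Serious, related to rucaparib, not an AESI | Not an SAE | Report | No |
| Serious, unrelated to both, not an AESI | Not an SAE | Report | No |
| Death not related to a procedure (and not from progression, which 8.4 excludes separately) | Outside the fatal-event reporting period | Report | No |
| AESI, serious or not | 8.4 addresses SAE status only | Report as AESI | Yes, as an AESI |

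The second row is the one that matters for safety. Section 8.8 sharpens it: every potential drug-induced liver injury that meets its criteria must be reported as an SAE, while 8.4 would deny SAE status to one arising in this interval.

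**Step 2. What the rules do if first dose means the first rucaparib dose ever, in the parent study.** Rollover consent then always follows first dose, no event can fall in the pre-dose period, and the carve-out has no effect for these patients.

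**Step 3. Which reading does the text support?** Sections 8.2 and 8.4 do not tie first dose to this study. Exclusion criterion 2b, section 4.4, section 7.3.2.2 and Table 7-1 footnote f do so explicitly, which suggests that the unqualified phrase might be meant differently. Against that, section 7.3 equates screening with the parent EOT visit, so the 8.4 reference to screening procedures makes sense only for entry into the rollover study. The text does not settle it: the clause is either inoperative or excludes drug-related events.

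**Step 4. How long is the interval?** It is the lead time from consent to the EOT visit (not stated) plus the gap from EOT to the next scheduled treatment visit (also not stated). Two assumptions bound the second part:

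- If the next visit is at most one cycle away, and cycles are 28 days (Table 7-1 footnote a), the gap is 0 to about 28 days.
- For women of childbearing potential, if one pregnancy test serves both as the EOT test (7.3) and as the test required within 3 days before first dosing (4.4), the gap is at most 3 days.

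Neither assumption is confirmed by the Protocol, and the consent lead time adds to both.

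**The case against.** The best defence is that the sections work together: 8.2 and 8.4 define an SAE, and 8.6 says when events so defined are reported. Procedure-related pre-dose SAEs would explain why 8.6 begins at consent, and 7.3.2.1 is worded as a limit and not as a duty to report everything. This softens the formal conflict. It does not remove the rule's failure to ask about rucaparib, the clash with 8.8, or the different start of the fatal-event period in 8.2.

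The second defence is that patients have already had their first dose, so the carve-out is empty and the opening of 8.2, which covers any dose, captures the event. That is a possible reading, but it leaves a clause with no effect that a site could still apply.

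Three stronger readings are tempting and are not supported:

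- A reader might infer that rucaparib's characteristic pulmonary and marrow events are lost. They are not: pneumonitis-type events are AESIs under 8.3, MDS and AML are treated as AESIs in 3.2.2 and 5.5.1.1, and 8.6 takes AESIs from consent.
- A reader might infer that every enrolled patient is affected. Patients entering only for long-term follow-up consent before their first follow-up visit in this study (7.2) and do not resume dosing, so they have no such interval.
- A reader might infer that events are certain to fall between the two studies. Inclusion criterion 1 requires current enrolment in a parent study of the same sponsor, whose reporting may cover part or all of the interval. Those protocols are not shown, and this one does not assign the interval to them.

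**Conclusion.** The concern holds in a limited form. For patients continuing treatment, the Protocol has two starting points for SAE reporting, and 8.2 and 8.4 use a procedure-only test in people already exposed to the drug. The consequence is confined to serious events that are not AESIs, between rollover consent and the first rollover dose, and it arises only if first dose means first dose in this study.

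The number of events cannot be estimated: the interval is not stated (0 to about 28 days after EOT under the one-cycle assumption, 3 days or less for some women, plus consent lead time), and parent-study reporting is unknown. It is a risk of non-reporting and of inconsistent reporting between sites, not a proven loss. No study estimate changes, since 9.4 plans no safety analysis; what is at stake is the stated objective of collecting SAEs and AESIs, and individual case reporting.

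**What to change.** Reconcile 8.2 and 8.4 with 7.3, 7.3.2.1 and 8.6:

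- Use one start of the reporting period, rollover informed consent, in every section, including the fatal-event period and the pre-dose parenthesis in 8.2.
- Delete the last bullet of 8.4, or limit it to events unrelated both to study procedures and to rucaparib, with rucaparib taken in the parent study expressly included. If the bullet is kept in that form, give the 8.2 parenthesis the same limit.
- Define first dose as the first dose in this study wherever the term remains.
- State how an event also reported under the parent study is cross-referenced, so that it is not counted twice. Do this without moving the start to the EOT visit, because consent comes before that visit and a second start point would recreate the conflict.

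The cost is a wording amendment, a few more SAE forms from the transition interval, and some possible duplicate reports to be matched.

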8.5 Pregnancy or Drug Exposure During Pregnancy

If a patient becomes pregnant during the study the investigator is to stop dosing with investigational product(s) immediately.

A pregnancy is not considered to be an AE or SAE; however, any pregnancy occurring in a study patient or partner of a study patient during study participation or within 6 months of the last dose for female patients, and within 3 months of last dose for partners of male study patients, must be reported to the sponsor using the Pregnancy Report Form within the same timelines as an SAE.

All pregnancies will be followed through to outcome, if possible. Once the outcome of the pregnancy is known, the Pregnancy Outcome Report Form is to be completed and reported to the sponsor.

AEs, SAEs, or AESIs that occur during pregnancy will be assessed and processed according to the AE or SAE/AESI processes using the appropriate SAE/AESI forms.

If any female partner becomes pregnant by a male study patient while he is receiving rucaparib, or within 3 months after the last dose of rucaparib, she will be asked to provide optional consent to allow follow-up until final outcome/delivery to determine if rucaparib has any effect on the pregnancy and fetal development.

8.6 Recording of Serious Adverse Events and Adverse Events of Special Interest

Any SAE/AESI that occurs after signing informed consent through 28 days after receiving the last dose of investigational product is to be reported to the sponsor and captured in the PV database.

After the 28-day Post-treatment Follow-up Visit, only SAEs assessed as potentially related to study drug should be reported per Clovis PV requirements and captured in the Clovis PV database. This includes serious reports of pneumonitis or associated events, if considered to be related to study drug.

After the 28-day Post-treatment Follow-up Visit, AESIs of MDS and AML, irrespective of causality, should be reported per Clovis PV requirements and captured in the Clovis PV database.

• AESIs of pneumonitis or associated events should only be reported up to, but not beyond, the Post-treatment Follow-up Visit (28-days after the last dose of rucaparib).

Information on the follow-up of SAEs, and AESIs is provided in Section 8.7.

In order to avoid vague, ambiguous, or colloquial expressions, the AE should be recorded in standard medical terminology rather than the patient's own words. Whenever possible, the investigator should combine signs and symptoms that constitute a single disease entity or syndrome into a final diagnosis, if appropriate. For example, fever, cough, and shortness of breath may be reported as pneumonia, if that is a reasonable diagnosis.

Each SAE is to be evaluated for causal relationship to the investigational drug, severity, and seriousness. The action taken, and the outcome must also be recorded.

SAEs and AESIs that occur during the study or within 28 days after receiving the last dose of investigational product, whether or not related to investigational product, must be reported immediately (ie, **within 24 hours** of knowledge of the event or additional information for a previously-reported event) to the sponsor/SAE designee. The contact information for reporting of SAEs/AESIs can be found on the SAE/AESI Reporting Form.

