3.2.2 Post-Treatment Phase

Upon treatment discontinuation in this study, regardless of reason (with the exception of withdrawal of consent or death), patients should return to the clinic for post-treatment safety monitoring assessments approximately 28 days (\pm 7) after the last dose of rucaparib has been administered in this study. Assessments should be performed per institutional standard of

care at the Post-treatment Follow-up Visit. Suggested assessments include monitoring for AEs, complete blood count, pregnancy test for WOCBP (required), disease assessments, laboratory assessments (clinical chemistry, urinalysis), vital signs, and rucaparib accountability (required). See Section 7.1.

The date and reason for treatment discontinuation should be captured in the eCRF.

Ongoing SAEs and AESIs at the time of the Post-treatment Follow-up Visit should be followed until resolution or stabilization has been determined, death, or loss to follow-up.

After the 28-day Post-treatment Follow-up Visit, only SAEs considered as potentially related to study drug should be reported per Clovis PV requirements and captured in the Clovis PV database. This includes serious reports of pneumonitis or associated events, if considered to be related to study drug.

After the 28-day Post-treatment Follow-up Visit, AESIs of myelodysplastic syndrome (MDS) and acute myeloid leukemia (AML), irrespective of causality, should be reported per Clovis PV requirements and captured in the Clovis PV database.

• AESIs of pneumonitis or associated events should only be reported up to, but not beyond, the Post-treatment Follow-up Visit (28-days after the last dose of rucaparib).

If a patient begins a subsequent anticancer therapy, the sponsor will terminate collection of SAEs.

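### All-causality SAE/AESI reporting ends at day 28 after the last dose in some sentences and at a visit allowed from day 21 in others, so after a visit on days 21-27 the same event is both required and excluded

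*Protocol*

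**What the plan says.** The protocol gives two ends for all-causality reporting.

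**Day count.**
- Section 8.6, first paragraph: "Any SAE/AESI that occurs after signing informed consent through 28 days after receiving the last dose of investigational product is to be reported".
- Section 8.6, last paragraph, applies the 24-hour limit regardless of causality: "SAEs and AESIs that occur during the study or within 28 days after receiving the last dose of investigational product, whether or not related".
- Section 7.3: "SAEs and AESIs that occur after informed consent will be collected through 28 days after the last dose of rucaparib for patients receiving treatment".
- Section 7.3.2.1: "Only SAEs and AESIs occurring from the time of informed consent through 28 days after the last dose of rucaparib will be reported". It starts the restricted SAE rule at the end of a window, not at a visit: "After the post-treatment 28-day follow-up window, only SAEs considered as potentially related to study drug should be reported". Section 8.7 also refers to the 28-day window.
- Section 8.2 sets a reporting period ending 28 days after the last dose and makes any event resulting in death within it reportable as an SAE.

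**Visit.**
- Section 8.6, second paragraph: "After the 28-day Post-treatment Follow-up Visit, only SAEs assessed as potentially related to study drug should be reported per Clovis PV requirements".
- Section 3.2.2: "After the 28-day Post-treatment Follow-up Visit, only SAEs considered as potentially related to study drug should be reported per Clovis PV requirements". Section 7.3 has a matching sentence, and Table 7-1 note e switches after the visit.
- Sections 3.2.2, 7.3, 7.3.2.1 and 8.6 each carry a bullet that stops pneumonitis-type AESIs at "the Post-treatment Follow-up Visit (28-days after the last dose of rucaparib").

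**Timing of the visit.** Section 3.2.2 and Table 7-1 note b place it about 28 days after the last dose, plus or minus 7 days. Note b also allows it on the discontinuation date if that is at least 28 days after the last dose.

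**The concern.** The two ends coincide only if the visit falls exactly on day 28. If it is earlier, a site that follows the visit sentence stops reporting unrelated SAEs while the day-count sentence still obliges it to report them.

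Collecting SAEs and AESIs is one of the three objectives in Section 2. Other AEs are monitored but not reported, and Section 9.4 plans no safety analysis, so the pharmacovigilance database is in effect the study's safety record. What is at stake is whether that record is complete and collected alike across sites. No planned estimate depends on it.

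**Working it through.** The protocol gives no figure to reproduce. The check is day arithmetic and a comparison of the sentences.

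**Inputs.** End by day count: day 28 after the last dose (8.6, 7.3, 7.3.2.1, 8.2). End by visit: day V of the Post-treatment Follow-up Visit (3.2.2, 7.3, 8.6, Table 7-1 note e; pneumonitis bullets also in 7.3.2.1). Visit tolerance: 7 days either side of day 28 (3.2.2, note b).

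**Permitted visit days.** 28 − 7 = 21 to 28 + 7 = 35, which is 15 days. Days 21-27 are 7 of these 15. This counts calendar days; it is not a share of patients.

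**Disputed stretch for an early visit.** Days V + 1 to 28, a length of 28 − V:

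| Visit day V | Disputed days | Length |
|---|---|---|
| 21 | 22-28 | 7 |
| 22 | 23-28 | 6 |
| 23 | 24-28 | 5 |
| 24 | 25-28 | 4 |
| 25 | 26-28 | 3 |
| 26 | 27-28 | 2 |
| 27 | 28 | 1 |
| 28 | none | 0 |

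The largest share of the window is 7/28 = 25%.

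**Example: visit on day 21, event on day 25.**
- *Unrelated SAE.* The first and last paragraphs of 8.6 require it; the second paragraph excludes it.
- *Unrelated death, not from progression.* Section 8.2 requires it as an SAE; the second paragraph of 8.6 excludes it. Deaths from progression are outside the point, because Section 8.4 does not treat progression as an SAE.
- *Non-serious pneumonitis.* The first paragraph of 8.6 requires it, and Section 8.3 makes it an AESI whatever its causality or severity. The bullet in 8.6 excludes it.
- *Related SAE, or MDS/AML.* Reportable under either rule, so there is no conflict. Section 3.2.2 separately ends SAE collection if a subsequent anticancer therapy starts.

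**Late visit (days 29-35, or later under note b).** The visit sentence says only what applies after the visit, and the pneumonitis bullet sets an upper limit. Neither requires all-causality reporting between day 28 and the visit, so neither contradicts an end at day 28. The end is unclear, no more.

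**The case against.** The best defence is that the protocol means day 28 throughout and that the 7 days are only a scheduling tolerance. The visit carries a 28-day label, the bullets gloss it as "the Post-treatment Follow-up Visit (28-days after the last dose of rucaparib"), and note e equates the two in parentheses. Section 8.2 defines the reporting period by day count, and the synopsis sets safety monitoring to 28 days after the last dose. In 8.6 the duty covering related and unrelated events is mandatory, while the visit sentence is only a should. This stands as evidence of intent and is why the fix adopts day 28. It does not remove the conflict: no sentence says which end governs when the visit is not on day 28, and note e is triggered by the visit itself.

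The consequence is also small. Date and cause of death go into the eCRF in any case, and no analysis is planned. That stands and limits the severity.

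Three stronger readings are tempting, but the text does not support them:
- *Late visits are a second contradiction.* They are not, for the reason shown in the working.
- *Note b, with the 42-day interruption in Section 5.5.1.1, opens a long contradictory gap.* Section 5.5.1.1 concerns the work-up of anemia, not the end of reporting. A late visit under note b leaves the end unclear at most.
- *The last paragraph of 8.6 imposes all-causality reporting on patients in long-term follow-up only.* It is a general 24-hour timing rule. The synopsis gives those patients a specific related-only rule, which reasonably prevails.

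**Conclusion.** The point holds as a minor inconsistency. For visits on days 21-27, the protocol both requires and excludes unrelated SAEs (including unrelated, non-progression deaths) and pneumonitis-type AESIs not reportable as related SAEs, when they occur after the visit and up to day 28. The stretch is 1 to 7 days per patient with an early visit. The day counts assume that sites use the full permitted window and that events are dated in whole days after the visit. The protocol gives neither event rates nor a distribution of visit days, so the number of affected reports cannot be stated. It would be wrong to infer a design flaw, a biased estimate, or that 7/15 of patients are affected.

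**What to change.** Use the protocol's own day count as the single cut-off:

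1. In Sections 3.2.2, 7.3, 7.3.2.1 and 8.6 and Table 7-1 note e, replace the phrases that start the restricted rule after the visit with *More than 28 days after the last dose of rucaparib*. In 7.3.2.1 this concerns the MDS/AML sentence.
2. End the pneumonitis bullets in 3.2.2, 7.3, 7.3.2.1 and 8.6 at 28 days after the last dose. A visit before day 28 then never ends reporting early.
3. Align the references to a window in 7.3.2.1, 8.7 and the synopsis with the same day count.

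Do not add an end tied to the date of treatment discontinuation; it would conflict with the reporting period in 8.2 and with the synopsis. Leave the 24-hour paragraph of 8.6 intact, including its coverage of events regardless of relatedness and of additional information on events already reported.

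The cost is a wording amendment, with the IRB/IEC approval that Section 10.7 requires. No visit, contact or data item is added.
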